5.1. Overview

In terms of randomization unit, the iCOMPARE study population is comprised of Internal Medicine training programs. In terms of entities providing data used to address the iCOMPARE hypotheses, iCOMPARE has 4 study subpopulations: the program directors leading the IM programs randomized to duty hour regimen, the faculty teaching at those programs, the trainees at those programs, and the patients cared for by faculty and trainees of these programs. iCOMPARE will obtain data both directly and indirectly from program directors, program faculty, and trainees (e.g., directly by survey or observation by iCOMPARE staff and indirectly by ACGME survey data shared with iCOMPARE) and indirectly from patients (e.g., patient data will be obtained from Medicare claims records).

5.2. Internal Medicine training programs

Because the outcomes for the patient safety and cost aims will be determined using Medicare data, the IM programs participating in iCOMPARE and experiencing the study duty hour standards must meet criteria relevant to Medicare patient volume. Because the treatment is applied at the IM program level, we need sufficient trainee presence in the care of these patients and hence participating programs must meet criteria related to program size. Table 15.4 displays a CONSORT style diagram of derivation of the iCOMPARE population of IM training programs. There are 379 IM training programs in the country. We applied the following eligibility criteria to identify programs that would be invited to apply:

1. At least one hospital with resident to bed ratio > 0.105 (excluded bottom 50% of hospitals by resident to bed ratio)
2. Sufficient Medicare patient volume (excluded bottom 25% of hospitals by patient volume)
3. In upper 75% of programs by program size

119 programs reflecting the bottom 50% in resident-to-bed ratio and the bottom 25% in patient volume related to the diagnoses in which mortality will be measured were excluded. Within the 260 programs that remained, the 65 in the lowest quartile of program size were excluded to ensure feasibility of obtaining sufficient trainee measurements. 195 remaining programs were eligible for recruitment to participate in iCOMPARE. Recruitment is discussed in Section 6. These 195 programs averaged about 30 interns, 25 PGY2 trainees, 25 PGY3 trainees, and 10 faculty per program.

5.3. Patients

Our study population for evaluation of patient safety and costs will be Medicare fee for service (FFS) beneficiaries at least age 65.5 years at hospital admission and admitted to one of the acute care hospitals affiliated with the randomized IM programs and at which the IM program implements the randomly assigned duty hour schedule between July 1, 2015 and June 30, 2016 and with any of the eligible principal diagnoses (see Table 15.5). These diagnoses apply to the majority of patients on a typical medical service and account for most of the deaths and other safety indicators. [26] While patients who are not Medicare beneficiaries are also cared for by trainees, 67.3% of patients on the medical services are Medicare beneficiaries and 72.2% of the mortality in medical admissions is in Medicare beneficiaries.[27, 28] The analyses are limited to FFS beneficiaries because CMS claims data are available for Medicare FFS patients only. All FFS Medicare patients will have complete, linked data: inpatient (Medicare Part A), outpatient, physician (Medicare Part B), and associated denominator files. Patients will be included if they were not enrolled in a managed care program six months before admission and one month post

discharge. The minimum age is 65.5 years and FFS status in the 6 months prior to admission is required so that claims are available for 6 months prior to the qualifying admission. The diagnoses were chosen to reflect the vast majority of patients on the typical IM service. Examining all patients, rather than just Medicare aged FFS patients, would be ideal but is not feasible because 30-day mortality, as well as the secondary outcomes, require 'linkable' data to events occurring outside the hospital, something not practical to obtain outside the Medicare system (i.e., it would be impractical to consent patients to be able to see their data, or to rely on numerous insurance companies or various state databases due to the scale of this trial). No patients will be excluded based on gender or race/ethnicity. We expect very little change in year to year demographic and clinical characteristics of the patients admitted to each hospital, as we observed in previous studies [9, 29].

We will address the change in ICD codes as follows. We will use the official crosswalk between the two coding systems and ensure that the principal diagnosis codes for the index admissions include all the possible codes identified in the crosswalk in both systems. Secondly we will have a separate dataset in which we will experiment and test the validity of the crosswalk, which is not part of the safety outcomes and cost analysis. This dataset will serve as the lab for the investigators to define the medical admissions in the ICD10 system in a way that is consistent with the ICD9. The lab data set will comprise patients admitted to hospitals affiliated with the remaining 137 eligible IM programs that did not elect to participate in iCOMPARE. This way we ensure that our experimental data are very similar to the data obtained for the programs participating in iCOMPARE. After we are satisfied with the validity of the crosswalk, we apply it to claims at hospitals affiliated with the randomized programs. It is helpful that the list of possible complications in medical admissions is limited.

5.4. Program directors, faculty and trainees

The directors, faculty and trainees affiliated with the participating IM programs will provide data to address iCOMPARE aims. All of these individuals are adult and there is no selection for gender or race/ethnicity. Depending on the aim being addressed, the iCOMPARE data collection focus may be all program directors, all program faculty, all trainees, all interns, or subsets of any of these or combinations of any of these.

5.5. Time and Motion Substudy

Six of the participating IM programs will be recruited to participate in the Time and Motion Substudy; the program director will consent to their program's participation in the Time and Motion Substudy. We will describe the substudy to all program directors and develop a list of those interested in participation. Within that list, in order to maximize efficiency, we will prioritize **Flex** programs with the largest numbers of interns on a **Flex** schedule per each rotation/block. Once the three **Flex** programs are identified, we will select three **Curr** programs from that list; the **Curr** programs must approximate key **Flex** program characteristics in terms of size, type of program, geography of program, and similarity of rotations. At each **Flex** site, we will randomly select 10 interns who are on **Flex** rotations for recruitment; we will continue to randomly select interns until 10 interns have consented to observations that will occur over a 2-4 week period. At the **Flex** sites we will recruit interns who are on **Flex** rotations. At the **Curr** sites we will identify the interns on rotations comparable to the **Flex** rotations and we will randomly select interns for recruitment from that pool. The only criteria for interns to be recruited into the substudy at a **Flex** IM program are being on a **Flex** rotation and consenting to participation (i.e., consenting to observation). The only criteria for interns to be recruited into the substudy at a **Curr** IM program are being on a rotation similar to a rotation observed at a **Flex** program and consenting to participation (i.e., consenting to observation).

5.6. Sleep and Alertness Substudy

From the IM programs that agreed to participate in the main protocol and that have already been randomized to **Curr** or **Flex**, we will identify comparable programs. These comparable programs will be asked to agree to also participate in the Sleep and Alertness Substudy. We plan to recruit 384 interns from participating IM training programs (50% randomized to **Flex**, 50% randomized to **Curr**) for the 14-day sleep and alertness evaluations (see section 6.4).

6. Recruitment

6.1. Recruitment of programs

The target for program enrollment in iCOMPARE was 58 IM programs in fall 2014. This timing allowed program staff to discuss the potential for iCOMPARE participation with prospective academic year 2015-2016 interns while they were interviewing for residency appointments and also sufficient time to prepare schedules meeting the **Flex** criteria if assigned to **Flex**. Starting in April 2014, CCC leadership began publishing the plan for iCOMPARE and soliciting program directors for interest and input. A presentation was made at the spring 2014 APDIM meeting and a summary description of iCOMPARE procedures and requirements was provided to interested program directors. Interested program directors could sign up for additional information by registering with the iCOMPARE website.

In summer 2014, the DCC and CCC sent application forms to interested program directors. The application form requested information regarding the hospitals at which the program planned to implement the iCOMPARE assigned duty hour schedule and acknowledgement of the responsibilities of participation. To confirm consent to participate at the program level, each program director was required to provide written institutional agreement to participate signed by the designated institutional official. Care was taken with the randomization of programs that operated in the same hospital to ensure that either the hospital would be active in iCOMPARE under only one of the programs or that the programs were randomized as a cluster. Based on program size data derived from the ACGME year book, these programs are estimated to have a mean of 30 interns and a mean of 50 PGY 2-3 trainees (residents).

Programs meeting randomization criteria were randomized to duty hour regimen starting in November 2014. Randomization ended in April 2015 with 63 IM programs randomized.

6.2. Recruitment of faculty and trainees

The recruitment process for IM programs involved the consent of the program director and the institution associated with the program, but did not involve consent of program faculty nor trainees in PGY2 or PGY3 years nor the incoming interns. While the individuals comprising these groups have no choice about their program's iCOMPARE participation, each of these individuals may opt in or out of individual participation in each iCOMPARE survey and in or out of substudy participation. Each iCOMPARE survey is prefaced with a statement that participation is voluntary and consent for the survey is assumed if the survey is completed. Recruitment of faculty and trainees in the main iCOMPARE protocol thus becomes an effort to solicit completion of surveys. Strategies to be employed to maximize participation in surveys include exhortatory emails from program directors, iCOMPARE leaders and others influential groups, and lottery type awards of token incentives (e.g., \$20 gift cards).

6.3. Recruitment of Time and Motion Substudy programs and interns

We will describe the substudy to all program directors and develop a list of those interested in participation. The program director will consent to his/her program's participation in the substudy.

Recruitment of interns for the substudy will be completed centrally so that program directors are not involved in consent of interns who are training under them. Program directors will be asked to provide

information to interns by way of presentations and to encourage participation but will not be part of the consent process and will not be privy to the electronic sign up sheet by which interns will initiate their individual recruitment for the substudy. Interns at the participating programs will also be recruited by email solicitation by iCOMPARE leaders. Interns will be asked to indicate interest and initiate the consent process by providing their contact information through an electronic application on the iCOMPARE website. Interns providing contact information will be sent the consent by a central substudy staff member; the central substudy staff member will review the consent with the intern during a telephone conversation. The intern will be asked to sign the consent statement electronically once all his/her questions have been answered. The intern will be provided with a copy of the signed consent statement. Interns who complete the Time and Motion Substudy data collection will receive a \$50 giftcard.

6.4. Recruitment of Sleep and Alertness Substudy programs and interns

From the IM programs that agreed to participate in the main protocol and that have already been randomized to **Curr** or **Flex**, we will identify comparable programs (50% randomized to **Flex**, 50% randomized to **Curr**). These comparable programs will be asked to agree to also participate in the Sleep and Alertness Substudy. From those programs agreeing to participate in the Sleep and Alertness Substudy, we will recruit a sample size of 384 interns (see power calculations) for the 14-day sleep and alertness evaluations.

Site coordinators and program directors will facilitate the interns' participation in the Sleep and Alertness Substudy, but they will be instructed not to influence whether an intern elects to participate or not participate in the Sleep and Alertness Substudy. Site coordinators will provide interns with an information package that includes the following items: (a) an information flyer that briefly summarizes the study, (b) the informed consent form (together with information on how to contact the study team with any questions), (c) a gift card worth up to \$140 (\$10/day for each day of completed Smartphone and actigraphy data), and (d) a pre-paid return envelope for mailing the consent form and the brief survey (alternatively, interns can hand the consent form and the brief survey to the site coordinator for mailing to the study team). Only site coordinators and the study team will know which interns consented to participate in the study. However due to the fact that interns have to wear actiwatches continuously during one 14-day period, they can be identified as study participants during this period (this is explicitly mentioned in the informed consent form). After written informed consent is received by the study team, the intern will be scheduled for a 14-day data collection period. In the week prior to this collection period, the study team will mail an actigraph, a Smartphone, and a copy of the informed consent form signed by both the intern and the study principal investigator to the site coordinator, who will hand them to the intern before the start of the data collection period. After the 14-day collection period, the intern will either return the equipment to the site coordinator who will mail it back to the study team or return it themselves in the prepaid envelope.

6.5. Recruitment of patients

Since patient data will be obtained exclusively through purchase of Medicare claims files from ResDAC, individual patients will not be contacted by iCOMPARE for consent nor for data collection – i.e., patients are not recruited for iCOMPARE participation.

7. Interventions

Participating IM programs will be assigned to one of the following groups:

1. The control schedule (**Curr**) reflects current duty hour standards established by ACGME.
2. The intervention schedule (**Flex**) has three conditions, each averaged over 4 weeks:
 - (1) work no more than 80 hours per week;
 - (2) call no more frequent than every third night;
 - (3) one day off in seven.

The ACGME has agreed to grant programs randomized to the **Flex** arm waivers from the current duty hour standards. The waiver applies to programs that meet the ACGME's standards for accreditation. While only IM programs in good standing with the ACGME could be randomized, there is potential for a program to lose that standing at any time during the conduct of the trial. Any **Flex** program that loses ACGME accreditation must revert to the **Curr** duty hour schedule as of the loss of accreditation, regardless of iCOMPARE participation or timeline.

The intervention period begins in July 2015 and ends in June 2016. While **Flex** programs are encouraged to use their **Flex** schedule on all rotations, each program has discretion to choose the rotations to which the **Flex** intervention will be applied. The intervention can be used on selected rotations (e.g., ICU only) instead of all rotations through which IM trainees cycle. All trainees rotating on services in the participating IM program are permitted to follow the duty hour rules assigned to the IM program by iCOMPARE. This includes rotators from other (non iCOMPARE) IM programs, as well as rotators from other departments, e.g. emergency medicine.

Program directors, faculty and trainees cannot be masked to intervention group. While there is no prohibition against discussion of iCOMPARE with patients, discussions are unlikely. Patients are likely to be masked to intervention group.

8. Randomization

The DCC generated the random treatment assignment schedule using SAS version 9.3. The randomization schedule was designed to yield an expected assignment ratio of 1:1 for **Curr** and **Flex** and employed a permuted block design, with block sizes documented at the DCC. Documentation of all these processes are retained at the DCC and are accessible only to authorized personnel. Adjustment for residual or other imbalances in the baseline composition of **Curr** and **Flex** groups, if needed, will be done using multiple regression techniques at the time of data analysis rather than through stratification in the design.

IM program eligibility was confirmed by the CCC, including receipt of institutional agreement to participate signed by the designated institutional official. After confirmation of eligibility, each IM program's ID was irrevocably linked to the next ordered treatment assignment using a program accessible to DCC personnel. If more than one program was to be randomized in a session, the set of programs to be randomized in the session was put in random order by a DCC staff member who was not the DCC staff member generating each program's treatment assignment. The data system automatically stored the date and time of assignment, the identity of the DCC staff person making the assignment, the program's ID, and the treatment assignment. Eligible programs that share a hospital were randomized together (i.e., to the same treatment group) because some residents will be rotating through both hospitals.

Treatment assignments were e-mailed to program directors at participating IM programs and posted on the iCOMPARE website.

9. Data collection

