iCOMPARE is a cluster randomized trial comparing two alternative duty hour standards for interns in 58 programs in Internal Medicine. The intervention programs will have less restrictive standards and will be compared to the current ACGMEmandated standards, which limits work duration to 16 hours. We will evaluate the extent to which the intervention programs preserve clinical and educational goals. Randomization is at the level of the Internal Medicine (IM) training program. The Data Coordinating Center (DCC) will randomize programs to control or intervention standards. Randomization will occur in the fall of 2014 to allow each program sufficient time to prepare training schedules. Assignment to duty hour schedule will be 11 and there will be no stratification. The ACGME has agreed to waive duty hour standards for participating programs. During the application process, each program must identify the hospitals affiliated with the program. All hospitals covered by a participating program are expected to participate. Exceptions are limited to hospitals that are covered by more than one participating program. A deadline (fall 2014) will be set for receipt of application materials from candidate training programs. The 58 selected programs are expected to include 4640 internal medicine residents: 1740 interns (approximately 30 interns per program) and approximately 1450 PGY2 trainees (approximately 25 PGY2 per program) and 1450 PGY3 trainees (approximately 25 PGY3 per program). Each program will include one program director (total of 58) and approximately 10 associated faculty (total of about 580 faculty). We will supplement the iCOMPARE data collected directly program from program directors with data collected on individuals and programs by national organizations (ACGME, ACP and APDIM). Patient safety (30day mortality) will be derived from Medicare claims database using methods proven in many other outcomes research studies by Drs. [name], [name] and his iCOMPARE team. The ACGME would grant programs randomized to the intervention arm waivers from the current duty hour standards. The three remaining standards would include: a. 1 day off in 7 averaged over 4 weeks, b. maximum of 80 hours/week of work, and c. inhouse overnight call no more frequent than q3 nights. All trainees rotating on services in the participating program would also be permitted to follow the duty hour rules of the internal medicine program. This includes rotators from other internal medicine programs as well as rotators from other departments, e.g. emergency medicine. To prevent the need for multiple programmatic schedule changes for intervention programs, and thus make the study feasible, the duty hour waivers will extend beyond the intervention year until action is taken by the ACGME on the duty hour policy. If action is not taken by 30 June 2019, the waivers will expire. Data are expected from the iCOMPARE study in calendar year 2018.

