11.2.2. Patient safety and costs

11.2.2.1.1. Patient safety hypothesis H1a - 30-day mortality

The primary outcome will be the difference in the pre-trial year and trial year mortality rates. The SD of the set of paired annual differences (2008 vs. 2007) in 30-day mortality from the preliminary data was equal to 1.5%. The mortality rates were similar across the two years: 11.1% and 11.5% for 2007 and 2008, respectively, consistent with minimal secular trends in mortality. The noninferiority sample size calculations described above show high power and low one-sided type-I error for the noninferiority hypothesis with a 1% margin.

The program level data needed for Specific Aim 1 outcome measures (patient safety and costs) will be aggregated into rates or other measures at the program level across two 1-year periods – the rates in the pre-trial year and the rates in the year of the trial. The outcome measure will be the change in these rates from the pre-trial year to the trial year and will be compared by treatment group using the same non-inferiority test proposed in the sample size justifications above.

The model (model A1) is:

$$Y_i = \gamma + \beta_1 x_i + \varepsilon_i, \quad i = 1, \dots, n_p \text{ where}$$

Y_i = Outcome measure in IM program i ,

γ = the intercept in the reference group (Curr),

β_1 = the difference in intercepts between Flex and Curr,

$x_i = 1$ if the i th IM program is in **Flex**, 0 if the i th IM program is in **Curr**

ε_i = i.i.d. random Gaussian errors with mean 0 and variance σ^2

n_p = Number of clusters (IM programs)

Tests of β_1 (or $\beta_1 - nim$, where nim is the noninferiority margin) estimated using linear regression will be used to test this hypothesis, since β_1 is the expected difference in outcome: **Flex** vs. **Curr**. All randomized programs will be included in this model and we expect no missing data.

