4.1 Patient safety hypothesis H1a – 30-day mortality

The primary outcome will be the difference between the pre-trial year and trial year 30-day mortality rates as described above.

The model (model A1) is:

$$Y_i = \gamma + \beta_1 x_i + \varepsilon_i, \quad i = 1, \dots, n_p \text{ where}$$

Y_i = Outcome measure in IM program i = Trial year rate - Pre-trial year rate,

γ = the intercept in the reference group (**Curr**),

β_1 = the difference in intercepts between **Flex** and **Curr**,

$x_i = 1$ if the i th IM program is in **Flex**, 0 if the i th IM program is in **Curr**

ε_i = i.i.d. random Gaussian errors with mean 0 and variance σ^2

n_p = Number of clusters (IM programs)

We will test β_1 (or $\beta_1 - nim$, where nim is the non-inferiority margin) ≤ 0 ; β_1 is the expected difference in outcome: **Flex** vs. **Curr**. All randomized programs will be included in this model and we expect no missing data.

The primary outcome measure for this cluster-randomized trial is the difference in 30-day mortality rates during the trial year versus the prior, which is 58 rate differences, 1 per randomized program, with a two-sample t-test for non-inferior patient mortality (difference no greater than 1%), comparing the **Flex** vs. **Curr** schedules. This approach permits the use of a simple model (two-sample non-inferiority t-test) for the set of at least $N=29$ pairs of trial year vs. pre-trial year differences in each group (**Curr** vs. **Flex**) in annual 30-day mortality rates following the paradigm elaborated by Hayes and Moulton (8) in their book on cluster randomized trials (CRTs). The model obviates the need for complex risk adjustment models, since it adjusts for secular trends in 30-day mortality that were common to all hospitals (e.g., severe flu season, technological improvements), as well as removing variation due to IM program population risk profiles (e.g., geography, patient characteristics) that are likely to cancel out by comparing successive years within IM program.

While these rate differences should adjust for most program to program differences in patient and institutional mix, we will also perform an important series of sensitivity analyses using risk-adjustment modeling methods that we developed (9) and which we will apply to the iCOMPARE data to confirm the findings of the primary analysis or to add a risk-adjustment caution to the statements of findings.

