4.1.1 Risk adjustment using aggregate predicted mortality

Briefly, sensitivity analyses will use iCOMPARE program-level risk-adjusted data on 30-day mortality by aggregating the patient-level risks derived from our fitted models. We will compute each patient's predicted 30-day mortality in the pre-trial period as we did in previous work (9-11). We will then average the predicted 30-day mortality for all patients in a program in the pre-trial period to obtain program i 's expected 30-day mortality rate in the pre-trial period, call it RA_{pi} , and average the predicted 30-day mortality for all patients in a program in the trial period to obtain what program i 's expected 30-day mortality rate would have been had these same patients been treated in the pre-trial period, which we call RA_{ti} . Then we update model A1 (at the program level) to include a term for the difference ($RA_{ti} - RA_{pi}$) so that the coefficient on treatment assignment is our estimate of being assigned to treatment versus not being assigned on the change in the outcome (e.g., mortality rate), adjusting for any changes in the risks of the patients at the program.

The model (Model B) is:

$$Y_i = \beta_0 + \beta_1 x_{1i} + \beta_2 x_{2i} + \varepsilon_i, \quad i = 1, \dots, n_p, \text{ where}$$

Y_i

= Mean outcome measure in IM program i (e.g., Trial year 30-day mortality - Pre-trial 30-day mortality)

$x_{1i} = 1$ if the i th IM program is in **Flex**, 0 if the i th IM program is in **Curr**

$x_{2i} = (RA_{ti} - RA_{pi})$

β_0 = Intercept for the IM programs

ε_i = i. i. d. random Gaussian errors with mean 0 and variance σ^2

n_p = Number of clusters (IM programs)

The adjusted non-inferiority tests will be t-tests based using the same non-inferiority margin (1%) and the estimates and standard errors for β_1 from the regression models. The model estimates, 95% CIs, and p-values will be derived using Stata, R or SAS.

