
4.1.3 Hierarchical models

We will do another sensitivity analysis using hierarchical logistic regression models for patient-level 30-day mortality in relation to fixed training program-level and patient-level risk factors **Flex** vs. **Curr**, year (trial vs pre-trial), **Flex** vs. **Curr** by year interaction and random effects to account for within-program correlations consisting of programs, hospitals, and patients. Hierarchical models are a different approach to risk adjustment and adjustment for within cluster correlation. We summarized our approach above. The key issues with such models relate to assumptions about the random effects (we assume Gaussian deviations in effects) and which effects are fixed, which are random, and which are both. These are difficult choices to make at the design phase.

However, hierarchical models do have appeal. For example, it is possible that there are things that affect a whole program or hospital in a specific year, e.g., a new program director is hired one year. The fixed

effects take account of program effects that are constant across all years of study, but not effects that are just present for one particular year. While we believe that single year effects will be rare and limited to a few hospitals, one approach would be to use robust standard errors that are clustered on training programs. This is the approach suggested by Angrist and Pischke (12) when there are at least 42 clusters, which is our setting. However, fitting a random effects model with random effects for program, hospital, attending, and patient would also be a way to account for these program*year effects, but probably harder to fit. Another issue relates to the few cases where one hospital has multiple programs in it so that there would be crossed random effects between program and hospital. In rare cases, a patient can be seen by two different programs at different times, this would also create crossed random effects. In principle, these configurations make the approach suggested above using robust standard errors that are clustered on program not fully valid as it would not take into account this crossing. Crossed random effect models are considerably harder to fit than nested random effect models, but it might be possible.

Despite, potential difficulties, we believe that hierarchical models will give us exploratory insights into our data and may help to understand effects or lack of effects arising from iCOMPARE.

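### Programs sharing a hospital could be randomised as one unit, but the primary mortality test treats every program as independent, which makes the non-inferiority test mildly anti-conservative if such units exist and are positively correlated.

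*Combined protocol and SAP*

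**What the plan says.** Two protocol sections describe how programs in the same hospital were handled.

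- Section 6.1 (Recruitment of programs) gives two routes: "either the hospital would be active in iCOMPARE under only one of the programs or that the programs were randomized as a cluster".
- Section 8 (Randomization) describes one: "Eligible programs that share a hospital were randomized together (i.e., to the same treatment group"). The reason given is that some residents rotate through both hospitals.

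The Procedures section of the IRB submission expects all of a program's hospitals to take part, and adds: "Exceptions are limited to hospitals that are covered by more than one participating program".

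The primary analysis is by program. SAP 4.1 describes the data as "which is 58 rate differences, 1 per randomized program", compared by a two-sample t-test. Model A1 (protocol 11.2.2.1.1 and SAP 4.1) assigns each program an independent, identically distributed Gaussian error and defines "n_p = Number of clusters (IM programs"). Model B (SAP 4.1.1) has the same error structure.

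Patients enter through hospitals. Protocol 5.3 takes admissions to affiliated hospitals "at which the IM program implements the randomly assigned duty hour schedule". Neither document says which program receives an admission when two programs share the hospital.

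The SAP raises the matter only in 4.1.3 (Hierarchical models): "Another issue relates to the few cases where one hospital has multiple programs in it". It adds that standard errors clustered on program would then not be fully adequate, and that crossed random effects might be feasible.

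**The concern.** Where the second route of section 6.1 was used, the programs concerned received one treatment assignment between them. They also share trainees and at least one hospital. Differencing trial year and pre-trial year removes stable hospital effects and trends common to all programs. It does not remove an event affecting one hospital in one year, and it does not remove the overlap created if a shared-hospital admission is counted in both programs' rates. Both would make the two changes positively correlated. Double counting is possible under the text but is not shown.

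A t-test that treats the two changes as independent overstates the information. The standard error is too small, so the upper confidence limit for Flex minus Curr falls below the 1% margin too often. The error therefore favours the claim that Flex is safe on mortality, which is the trial's only primary hypothesis. SAP 4.1.3 recognises shared hospitals as a problem for a sensitivity analysis, but the primary test makes the stronger assumption of full independence and carries no caution.

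There is a separate, smaller gap in SAP 4.1.2. The patient-level logistic model has program and year fixed effects but no committed clustered variance; 4.1.3 mentions clustered errors only as one option. The documents do not allow that gap to be sized.

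**Working it through.** **Inputs from the documents.** Margin 0.01, SD of a program's change 0.015, one-sided alpha 0.05 and 1:1 allocation (protocol 11.1 and 8); 63 programs randomised (protocol 6.1).

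**Inputs that are assumed.** The number of joint pairs, k, and the correlation between the two changes in a pair, ρ. Neither is given; the SAP says only that such hospitals are few. The range used is k = 2, 3, 5 and ρ = 0, 0.3, 0.5, 1.0.

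**Step 1: reproduce the plan's power.** With n₁ and n₂ programs, df = n₁ + n₂ − 2 and non-centrality = 0.01 / [0.015 √(1/n₁ + 1/n₂)].

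- 29/29: non-centrality 2.539, power 0.8059, as stated.
- 40/40: non-centrality 2.981, power 0.9050, as stated.

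**Step 2: variance of the arm contrast.** With k same-arm pairs among N programs of equal variance, the true variance exceeds the independence value by a factor of about

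R = 1 + 2kρ/N.

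For N = 63:

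- k = 2, ρ = 0.3: 1 + 1.2/63 = 1.019
- k = 3, ρ = 0.5: 1 + 3/63 = 1.048
- k = 5, ρ = 1.0: 1 + 10/63 = 1.159

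**Step 3: true type I error.** The critical value on 61 df is 1.670. The actual error is approximately P(T₆₁ > 1.670/√R). For k = 3 and ρ = 0.5, 1.670/√1.048 = 1.632, which gives 5.4%.

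| Joint pairs | ρ = 0 | ρ = 0.3 | ρ = 0.5 | ρ = 1.0 |
|---|---|---|---|---|
| 2 | 5.0% | 5.2% | 5.3% | 5.5% |
| 3 | 5.0% | 5.2% | 5.4% | 5.8% |
| 5 | 5.0% | 5.4% | 5.7% | 6.3% |

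**Step 4: simulation check.** The planned t-test was simulated at the margin, 200,000 trials per setting, with pairs always assigned to the same arm. With 63 programs, 5 pairs and ρ = 0.5, the program-level test rejected in 5.7% of trials. One averaged change per randomised unit brought this to 5.0%. Across all settings with pairs, the unit-level test stayed between 4.9% and 5.1%.

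**Step 5: power by randomised unit.** Keeping SD 0.015 per unit:

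| Units | Joint pairs among 63 programs | Power |
|---|---|---|
| 63 | 0 | 0.834 |
| 60 | 3 | 0.818 |
| 58 | 5 | 0.806 |
| 57 | 6 | 0.7996 |

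These are slightly pessimistic when ρ is below 1, because averaging two programs reduces that unit's variance. The critical t barely moves: 1.670 with 63 units and 1.673 with 58.

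**The case against.** The strongest reply is that the effect is too small to matter. With two or three pairs and ρ of 0.3 to 0.5, the error is 5.2% to 5.4%. Reaching 6.3% takes five pairs and perfect correlation. Power stays above 0.80 until there are six pairs, because 63 programs were randomised against 58 required.

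High correlation is also hard to reach without double counting. Binomial noise in two separate sets of patients is independent. At 11% mortality, the binomial SD of a one-year change is √(2 × 0.11 × 0.89 / n). For an assumed 860 admissions per program-year this is about 1.5%, which is the whole of the plan's SD; for 1,720 it is about 1.07%, leaving roughly half the variance free to correlate. Programs often span several hospitals, so one shared hospital dilutes the correlation further.

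There may also be no joint units at all: section 6.1 allows a shared hospital to be active under one program only, and the exception in the IRB submission is consistent with that. Finally, SAP 4.1.3 commits to a sensitivity model with random effects for programs and hospitals.

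Much of this stands. The effect is small, ρ = 1 is an outer bound, and the number of joint units is unknown. A negative correlation would reverse the direction. What remains is that section 8 reports joint randomisation as done, the primary test ignores it, and the hospital random effect belongs to an analysis the SAP calls exploratory, so it does not correct the primary standard error.

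**Conclusion.** The concern holds in its conditional form. If jointly randomised programs exist and their mortality changes are positively correlated, the planned test is mildly anti-conservative: about 5.2% to 5.4% for two or three pairs at ρ of 0.3 to 0.5, and 6.3% at the far end of the assumed range (five pairs, ρ = 1). If either condition fails, there is no inflation. Both k and ρ are assumptions, and the calculation takes joint units to be pairs of programs with equal variance.

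The plan's stated power is arithmetically correct. On this range the point does not undermine the design. It should still be corrected, because the bias runs toward the safety claim on the primary outcome and the correction costs very little.

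**What to change.** In SAP 4.1 and 4.1.1:

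1. State how many randomised units contain more than one program. If there are none, one sentence to that effect settles the primary analysis.
2. State the rule that attributes each admission at a shared hospital to one program or unit, once.
3. Base the test on the randomised unit, by either (a) one pooled change per unit with df = units − 2, or (b) one change per program with standard errors clustered on the randomised unit and small-sample degrees of freedom. Both bring the type I error back to about 5%.
4. Restate power on the number of randomised units.

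In SAP 4.1.2, commit to standard errors clustered on the randomised unit.

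The cost is SAP wording and a grouping variable that the data coordinating center should hold, since it made the assignments. A few degrees of freedom are lost and intervals may widen slightly. Option (a) gives a joint unit one weight instead of two, which departs from the stated outcome of one change per program; option (b) keeps that outcome.
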